7.2.1.1 Reconstitution

The drug product should be reconstituted and processed under aseptic conditions (i.e. qualified laminar flow unit and trained personnel) to preclude microbial contamination.

Using a sterile syringe, gently add 11.9 mL of water for injection through the middle of the stopper to the freeze-dried product into the 30 mL injection vial to obtain a solution (approximate reconstituted volume is 12.5 mL). During reconstitution, make sure that the needle does not come into contact with the cake or resulting solution; avoid shaking. The lyophilizate should dissolve completely.

The reconstituted lyophilizate may be diluted only after the solution is clear.

Dilution of the reconstituted solution

Dilution of the reconstituted solution with 0.9% sodium chloride solution (normal saline) should be done under aseptic conditions (i.e. qualified laminar flow unit and trained personnel) to preclude microbial contamination. A slight turbidity may occur during the dilution which does not affect the quality of the drug product. Pharmacy will consider the use of inline filters for subsequent administrations.

Stability of the reconstituted solution

Exposure to bright light should be avoided; standard room illumination does not necessitate any precautions.

The reconstituted solution is physically and chemically stable for 24 h at room temperature and between 2°C and 8°C. However, unless administered immediately, for microbiologic consideration, the reconstituted solution should be stored between 2°C and 8°C and used within 6 h according to USP 797 “Pharmaceutical Compounding – Sterile preparations”. If not reconstituted under aseptic conditions, the solution should be used immediately or stored at 2°C to 8°C and used within 1 h, according to USP 797.

If frozen or stored above 25°C (77°F), the solution should be discarded.

Stability of the diluted solution

Exposure to bright light should be avoided; standard room illumination does not necessitate any precautions.

Stability investigations have shown that if diluted under aseptic conditions, concentrations between 0.1 and 3.0 mg/mL are stable for the period of use (24 h) at room temperature and between 2°C and 8°C. However, unless administered immediately, for microbiologic consideration, diluted solution should be stored between 2°C and 8°C and used within 6 h according to USP 797 “Pharmaceutical Compounding – Sterile preparations”.

If not diluted under aseptic conditions, the solution should be used immediately or stored at 2°C to 8°C and used within 1 h, according to USP 797.

If frozen or stored above 25°C, the solution should be discarded.

Refer to IB for anetumab ravtansine for details regarding drug properties and formulation.

7.3 Dosage and administration

7.3.1 Administration of anetumab ravtansine

After reconstitution and dilution (as described in Section 7.2.1), anetumab ravtansine will be administered as a 1-hour IV infusion every 3 weeks on Day 1 of each 21-day cycle until confirmed radiological PD by RECIST 1.1, clinical progression as assessed by investigator, or any other criteria for withdrawal of treatment.

The individual dose will be 6.5 mg/kg per infusion from Cycle 1 onwards. In obese patients, anetumab ravtansine dose should be calculated considering a maximum weight of 100 kg.

Strict IV administration has to be ensured to avoid local intolerance reactions. After completion of the 1-hour anetumab ravtansine infusion, the infusion line will be rinsed with ≥ 100 mL of 0.9% saline solution to be administered as a short infusion.

See Section 9.1 for details on scheduled administrations.

7.3.2 Dose modification

The NCI-CTCAE v4.03 will be used to assess toxicities; in addition, a Bayer grading system (see **Table 2-6** and **Table 2-7**) will be used to assess corneal toxicity.

TEAE requiring dose modification (temporary treatment interruption, dose reduction, or permanent discontinuation of treatment) will be defined as any of the events described below that is possibly, probably, or definitely related to anetumab ravtansine and occurs anytime during the study (not only in Cycle 1).

The dose reduction levels of anetumab ravtansine will follow pre-defined dose levels shown in **Table 2-2**.

Dose level 1 (starting dose):	6.5 mg/kg Q3W
Dose level -1:	5.5 mg/kg Q3W
Dose level -2:	4.5 mg/kg Q3W

Q3W = Every 3 weeks

7.3.2.1 Hematological toxicities

Dose modifications for hematological toxicity

- If treatment modification is required due to a hematological TEAE, and the continuation of treatment is appropriate, the anetumab ravtansine dose will be adjusted as described in **Table 2-3** and **Table 2-4** below.
- G-CSF and other hematopoietic growth factors may be used during the study in the management of acute toxicity such as febrile neutropenia when clinically indicated per ASCO Recommendations for Therapeutic Use of CSF (26) or at the discretion of the investigator; however, they may not be substituted for a required dose reduction.
- Blood transfusions and therapy with IV or subcutaneous erythropoietin-stimulating agents (epoetin alpha, darbepoetin alpha) are allowed per institution guidelines but may not be used as substitute for a required dose reduction (see also **Table 2-8**).
- Platelet transfusion may be used during the study in the management of acute toxicity such as hemorrhage or bleeding events, however they may not be used as substitute for a required dose reduction.

Table 2-3: Dose adjustments in response to neutrophil and platelet nadir ^a counts of the previous cycle

Absolute neutrophil nadir count of the previous cycle (/mm³)		Platelet nadir count of the previous cycle (/mm³)	Anetumab ravtansine dose adjustment ^b
≥ 500 or < 500 for < 7 days	and	≥ 25,000	No change
< 500 for ≥ 7 days	and/	< 25,000 regardless of the presence of active bleeding (or ≥ 25,000 with clinically significant bleeding, i.e. bleeding requiring platelet transfusion)	Decrease 1 dose level ^b
Febrile neutropenia ^c	and/	< 25,000 regardless of the presence of active bleeding (or ≥ 25,000 with clinically significant bleeding, i.e. bleeding requiring platelet transfusion)	Decrease 1 dose level ^b

ANC = Absolute neutrophil count; C = Cycle; CBC = Complete blood count; D = Day; Q3W = Every 3 weeks

- a Site visits and blood test for CBC (and biochemistry) on D8 and D15 will be performed on C1, C2 and C3 only. From Cycle 4 onwards, visits and procedures on D8 and D15 are no longer required.
- b Dose reduction by 1 dose level translates to a change from 6.5 mg/kg Q3W to 5.5 mg/kg Q3W, or from 5.5 mg/kg Q3W to 4.5 mg/kg Q3W. Not more than 2 dose reductions from the starting dose level are permitted.
- c Febrile neutropenia is defined as ANC < 1000/mm³ and fever (a single body temperature reading of > 38.3°C [101°F] or a sustained body temperature of ≥ 38°C [100.4°F] for more than 1 hour).

Clinical Study Protocol

19-September-2018

BAY 94-9343 (Anetumab in Pancreatic Cancer)
Version 4.0

Page: 28 of 77

Table 2-4: Dose adjustments in response to pre-infusion values

Absolute neutrophil count (/mm ³)	Platelets (/mm ³)	Hemoglobin (g/dL)	Treat	Anetumab ravtansine dose adjustment
≥ 1,000	and	≥ 75,000	Treat on time	Adjust dose by nadir ^a counts in previous cycle per investigator's discretion
< 1,000	and	< 75,000	Delay until ANC ≥ 1.0 and platelets ≥ 75,000 ^b	Decrease by 1 dose level ^c
		< 8	Delay until Hb ≥ 8 ^b	Re-start at the same dose or decrease by 1 dose level ^c (at investigator's discretion)

ANC = Absolute neutrophil count; C = Cycle; CBC = Complete blood count; D = Day; Hb = Hemoglobin; Q3W = Every 3 weeks; TEAE = Treatment-emergent adverse event

- a Site visits and blood test for CBC (and biochemistry) on D8 and D15 will be performed on C1, C2 and C3 only. From Cycle 4 onwards, visits and procedures on D8 and D15 are no longer required.
- b Treatment will be discontinued if the TEAE fails to resolve to Grade ≤ 1 (or Hb ≥ 9 g/dL in case of anemia) within 6 weeks after the last dose of anetumab ravtansine.
- c Dose reduction by 1 dose level translates to a change from 6.5 mg/kg Q3W to 5.5 mg/kg Q3W, or from 5.5 mg/kg Q3W to 4.5 mg/kg Q3W. Not more than 2 dose reductions from the starting dose level are permitted.

7.3.2.2 Non-hematological toxicities**Non-hematological toxicities requiring dose or infusion modification**

- CTCAE Grade 2 or Grade 3 anetumab ravtansine infusion reaction or other CTCAE Grade 2 or Grade 3 hypersensitivity events (see Section 7.3.2.1.3)
- AST and/or ALT increase > 5.0 x ULN (CTCAE Grade ≥ 3)
- AST and/or ALT increase > 3.0 x ULN (CTCAE Grade ≥ 2) with concomitant increase in total bilirubin > 1.5 x ULN (CTCAE Grade ≥ 2)
- Total bilirubin > 3.0 x ULN (CTCAE Grade ≥ 3)
- Bayer Grade ≥ 3 corneal toxicity (see below and **Table 2-6**)
- Any other Grade ≥ 3 non-hematological toxicity that, in the investigator's opinion, warrants treatment modification (see **Table 2-5**), **excluding** the following:
 - Nausea, vomiting, or diarrhea if manageable with anti-emetics or antidiarrheals within 7 days
 - Hair loss
 - Fatigue lasting ≤ 72 h
 - Certain asymptomatic laboratory assessments without a clear clinical correlate, if the investigator determines that this TEAE would not require treatment modification
- Any other toxicity irrespective of the type or severity that represents a clinically significant risk to patient in the investigator's opinion.

Dose modifications for non-hematological toxicity

If treatment modification is required due to a **non-hematological TEAE** as listed above, other than corneal toxicity and infusion reaction/hypersensitivity events, and the continuation of treatment is appropriate, the anetumab ravtansine dose will be either reduced or maintained as is at investigator's discretion (see **Table 2-5**).

Table 2-5: Dose adjustments in response to non-hematologic toxicities

CTCAE v4.03 grade	Anetumab ravtansine dose delay / interruption	Anetumab ravtansine dose modification
Grade 1 – 2 ^a	Treat on time	No change required (at investigator's discretion)
Grade 3	1 st appearance: Delay/Interruption until Grade ≤ 2 ^b	Re-start at the same dose or decrease by 1 dose level ^c (at investigator's discretion)
	2 nd appearance: Delay/Interruption until Grade ≤ 2 ^b	Decrease by 1 more dose level ^c
	3 rd appearance: Permanently discontinue	
Grade 4	Permanently discontinue	

ALT = Alanine aminotransferase; AST = Aspartate aminotransferase; CTCAE = Common Terminology Criteria for Adverse Events; Q3W = Every 3 weeks; TEAE = Treatment-emergent adverse event

- a AST and/or ALT increase of CTCAE Grade 2 with concomitant increase in total bilirubin of CTCAE Grade 2 will be treated as a CTCAE Grade 3 event.
- b Treatment will be discontinued if the TEAE fails to resolve to Grade \leq 1 within 6 weeks after the last dose of anetumab ravtansine.
- c Dose reduction by 1 dose level translates to a change from 6.5 mg/kg Q3W to 5.5 mg/kg Q3W, or from 5.5 mg/kg Q3W to 4.5 mg/kg Q3W. Not more than 2 dose reductions from the starting dose level are permitted.

The anetumab ravtansine dose reduction due to non-hematological TEAE will be done as described below:

- If the patient experienced a TEAE requiring dose reduction at the 6.5 mg/kg Q3W dose level, the subsequent anetumab ravtansine dose should be reduced to 5.5 mg/kg Q3W.
- If the patient experienced a TEAE requiring dose reduction at the 5.5 mg/kg Q3W dose level, the subsequent anetumab ravtansine dose should be reduced to 4.5 mg/kg Q3W.

After dose reduction, there could be no intra-patient dose escalation irrespective of the type of TEAE that has led to dose reduction in this patient.

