- Patient starts treatment with any other anti-cancer therapy or any other prohibited medication as per Section 8.1.
- Positive serum β -HCG test consistent with pregnancy. Pregnancy should be reported along the same timelines as an SAE.
- Use of illicit drugs or other substances that may, in the opinion of the investigator or his designated associate(s), have a reasonable chance of contributing to toxicity or otherwise confound the results.
- Development of any intercurrent illness or situation which may, in the judgment of the investigator, affect assessments of clinical status and study endpoints to a relevant degree.
- Lost to follow-up.
- Death.

Patients must be withdrawn from **treatment with anetumab ravtansine** if any of the following occurs:

- CTCAE Grade 4 non-hematological AE and Bayer Grade 4 corneal toxicity (see Table 2-6) (except at the investigator's discretion in case of certain Grade 4 abnormality of laboratory assessments, such as abnormal laboratory assessments without corresponding clinical symptoms, or abnormal laboratory assessments that can be easily clinically managed).
- If any type of TEAE requiring dose modification does not resolve to Grade ≤ 1 (or Hb ≥ 8 g/dL in case of anemia) within 6 weeks after the last dose of anetumab ravtansine.
- Delay in anetumab ravtansine administration of 3 weeks (max. 6 weeks between 2 infusions of study drug).
- TEAE requiring dose reduction when already at the 4.5 mg/kg Q3W dose level (minimum dose).
- More than 2 dose reductions required due to a TEAE.

AE = Adverse event; β -HCG = β subunit of human chorionic gonadotropin; CTCAE = Common Terminology Criteria for Adverse Events; Hb = Hemoglobin; RECIST = Response Evaluation Criteria in Solid Tumors; PD = Progressive disease; Q3W = Every 3 weeks; SAE = Serious adverse event; TEAE = Treatment-emergent adverse event

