7.3.2.4 Continuation of treatment with anetumab ravtansine

Treatment with anetumab ravtansine could be re-started at the appropriate dose if the TEAE requiring dose modification has resolved to Grade < 2 within 6 weeks after the last dose of anetumab ravtansine.

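### The six-week stopping rule for anemia uses Hb ≥ 9 g/dL in Table 2-4 but Hb ≥ 8 g/dL in Figure 2-1; whether the Table 2-3 nadir reductions are mandatory also needs clarifying

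*Combined protocol and SAP*

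**What the plan says.** **Anemia.** Footnote b of Table 2-4 requires discontinuation unless the event resolves to Grade ≤ 1, or to "Hb ≥ 9 g/dL in case of anemia) within 6 weeks after the last dose of anetumab ravtansine". Figure 2-1, in its list of mandatory withdrawals from study drug, gives the same rule with "Hb ≥ 8 g/dL in case of anemia) within 6 weeks after the last dose of anetumab ravtansine". The third row of Table 2-4, whose cell carries footnote b, sets the re-start condition as "Delay until Hb ≥ 8". Inclusion criterion 8 in Section 6.1.2 admits patients at 8 g/dL or above. Section 7.3.2.4 permits re-starting if the event "has resolved to Grade < 2 within 6 weeks after the last dose of anetumab ravtansine" and gives no hemoglobin alternative. Figure 2-1 also withdraws a patient for "Delay in anetumab ravtansine administration of 3 weeks (max. 6 weeks between 2 infusions of study drug".

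**Nadir counts.** After febrile neutropenia, a prolonged neutrophil nadir or a low platelet nadir, Table 2-3 instructs "Decrease 1 dose level" and mentions no discretion. The text of Section 7.3.2.1 says of growth factors that "they may not be substituted for a required dose reduction". The first row of Table 2-4 covers patients whose Day 1 counts have recovered. It ties the dose to nadir "counts in previous cycle per investigator" discretion.

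**The concern.** Footnote b and Figure 2-1 are both mandatory and give different limits for one decision. Nothing in the protocol says which governs: Section 7.3.2.5, which should direct the reader to the withdrawal criteria, points to the section on full screening failure. Two sites that each follow the protocol could therefore stop one patient and continue another in the same state.

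On nadir counts, a patient who has had febrile neutropenia and recovered by Day 1 could be reduced at one site and re-treated at full dose at another. That is a patient-safety question. Both points also touch reporting, because toxicity is a secondary objective and Section 10.2.2.2 summarizes discontinuations and dose reductions due to adverse events.

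**Working it through.** This is a comparison of rules; the plan has no figure to reproduce.

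**Step 1. Set the anemia limits side by side.**

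| Place | Decision | Hemoglobin limit |
|---|---|---|
| Table 2-4, footnote b | permanent stop | 9 g/dL |
| Figure 2-1 | permanent stop | 8 g/dL |
| Table 2-4, row 3 | re-start after delay | 8 g/dL |
| Section 6.1.2, criterion 8 | entry | 8 g/dL |
| Section 7.3.2.4 | re-start | none, grade only |

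Only the first two rows are like for like: both are stopping rules, with the same grade condition and the same six-week clock from the last dose. They differ by 9 − 8 = 1 g/dL, so the disputed band runs from 8.0 to just under 9.0. For whole-number grades, the condition in Section 7.3.2.4 is the same as Grade ≤ 1; what that section lacks is the hemoglobin alternative.

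**Step 2. Find when the band matters.** Cycles last 3 weeks and infusions may be at most 6 weeks apart, so the longest delay is 6 − 3 = 3 weeks.

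- Before week 6, row 3 lets a patient at 8.0 to 8.9 be re-dosed. On the natural reading, that infusion becomes the new last dose and restarts the clock.
- A patient not re-dosed by about week 6 is withdrawn under the delay limit, whatever the hemoglobin.
- What remains is the patient who reaches the band only near week 6. Footnote b stops this patient permanently; the anemia rule in Figure 2-1 does not.

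**Step 3. An illustrative patient.** Hemoglobin is 8.5 at entry (allowed), falls below 8 on treatment and is back at 8.5 near week 6. The patient has returned to baseline, meets the row 3 re-start limit and passes Figure 2-1, yet fails footnote b.

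**Step 4. The nadir rule.** A one-level reduction from the starting dose is 6.5 − 5.5 = 1.0 mg/kg, and 1.0 / 6.5 = 15%. Section 7.3.2.2 bars re-escalation whatever the type of event, so the difference can persist. At 4.5 mg/kg, Figure 2-1 withdraws a patient who has an event requiring reduction, so there the choice is between stopping and continuing. Day 8 and Day 15 counts are scheduled only in Cycles 1 to 3, so scheduled nadirs inform three doses (Day 1 of Cycles 2, 3 and 4). Febrile neutropenia can raise the question in any cycle.

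**Step 5. Effect on reporting.** One patient handled differently moves a discontinuation or reduction percentage by 1/30 = 3.3 points, or by 1/20 = 5.0 points if the trial stops after the first stage.

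**The case against.** The strongest reply is that the anemia conflict seldom changes anything. Row 3 and the delay limit together leave only a narrow window near week 6. The rules cover only events at least possibly related to the drug. Transfusion and erythropoiesis-stimulating agents are allowed during treatment and may lift a patient past either limit. All of this stands. A reader might infer that every patient at 8.0 to 8.9 g/dL faces opposite outcomes; Step 2 shows that the documents do not support that. The two stopping limits still disagree.

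On nadir counts, a reader might infer a flat contradiction between Tables 2-3 and 2-4. The documents do not go that far. The lead-in in Section 7.3.2.1 is conditional on a modification being required and sends the reader to both tables. Row 1 refers back to nadir counts, and it also covers patients with no Table 2-3 event, so its discretion may be meant for them. That reading is possible but not stated, and it sits awkwardly with an instruction that offers no choice and a reduction described as required. This is an ambiguity to clarify.

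A reader might also try to size the problem from the dose reductions in the 6.5 mg/kg expansion cohort in Section 3.1. Those counts cover reductions from all causes in ovarian cancer and mesothelioma. They measure neither anemia discontinuations nor nadir-driven reductions.

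**Conclusion.** The anemia inconsistency is real and should be corrected. One mandatory rule carries two limits 1 g/dL apart, and the re-start cell and the entry criterion suggest that 9 is the outlier. Its reach is limited to patients still recovering near week 6. The documents give no rates of anemia or neutropenia, so I put no number on patients affected; it is probably small.

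The nadir wording is a secondary clarification, worth making because it concerns re-dosing after febrile neutropenia.

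The Simon two-stage limits, error rates and primary endpoint depend on neither point.

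This rests on two readings: that a re-dose resets the six-week clock, and that the joining word between the columns of Table 2-3, which is cut short in the available text, means and/or. A patient with both a neutrophil and a platelet event meets the ambiguity on either reading. The neutrophil limit printed as 1.0 in row 2 of Table 2-4, under a per-mm³ heading, plainly means 1,000 and is only a typo.

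**What to change.** 1. **Table 2-4, footnote b:** change the limit to Hb ≥ 8 g/dL, to agree with Figure 2-1. If the clinical team intends 9, change Figure 2-1 and the row 3 re-start limit to 9 instead, and say how this applies to patients who enter between 8 and 9.
2. **Section 7.3.2.4:** add the same hemoglobin alternative for anemia, at whichever value is chosen.
3. **Table 2-4, row 1:** subject to the clinical team confirming that the Table 2-3 reductions are mandatory, reword along these lines: *apply the Table 2-3 reduction after a Table 2-3 nadir event; otherwise at the investigator's discretion.* If they are not meant to be mandatory, say so in Table 2-3.
4. **Table 2-4, row 2:** print the neutrophil limit as 1,000/mm³ in the same edit.

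The cost is a few words in one table, one footnote and one sentence (also Figure 2-1 if 9 is chosen, or Table 2-3 if its reductions are discretionary), with no added tests, visits or patients.

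### Section 7.3.2.2 has no single rule for recurrent Grade 3 non-hematological toxicity: the lead-in sentence, Table 2-5, the step-down bullets and Figure 2-1 do not agree

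*Combined protocol and SAP*

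**What the plan says.** Four places in the protocol bear on a Grade 3 non-hematological toxicity that comes back.

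- **Lead-in sentence, Section 7.3.2.2.** For listed non-hematological events needing modification, "the anetumab ravtansine dose will be either reduced or maintained as is", at the investigator's discretion, with a reference to Table 2-5. Its scope is limited to events "other than corneal toxicity and infusion reaction/hypersensitivity events, and the continuation of treatment is appropriate". It does not distinguish a first event from a later one.
- **Table 2-5, Grade 3 rows.** First appearance: "Re-start at the same dose or decrease by 1 dose level", marked as discretionary. Second appearance: "Decrease by 1 more dose level", with no discretion marked. Third: "appearance: Permanently discontinue". Note c caps the number of reductions at two.
- **Step-down bullets below Table 2-5.** These go by the dose at which the event occurred. For an event requiring reduction at 6.5 mg/kg the next dose is 5.5 mg/kg; for one "at the 5.5 mg/kg Q3W dose level, the subsequent anetumab ravtansine dose should be reduced to 4.5 mg/kg Q3W".
- **Figure 2-1, Section 6.3.2.** The anetumab-specific list stops treatment for Grade 4 events, failure to resolve within 6 weeks, a 3-week delay, a reduction needed at 4.5 mg/kg, or more than two reductions. A third Grade 3 appearance is not on it. The general list has an unacceptable-toxicity item that refers back to Section 7.3.2.

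**The concern.** The lead-in grants a choice that the table it cites withdraws from the second appearance onward. The second-appearance cell speaks of one *more* level, which presumes an earlier reduction, yet the first-appearance row allows a re-start without one. The table counts appearances while the bullets look at the current dose, and these two ways of tracking a patient separate once someone has been re-started at an unchanged dose. The list a site would consult for stopping rules does not carry the table's third-appearance stop.

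Sites could therefore manage the same event differently, which is first a safety matter. It also affects reporting. Toxicity is a secondary objective (Section 4), and Section 10.2.2.2 commits to summarizing the number and percentage of patients who discontinue, or need a reduction or interruption, because of an adverse event. In a trial of at most 30 patients at 2-3 centers, those counts would partly reflect which sentence each site followed.

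**Working it through.** The plan gives no figure on this point, so the check is a trace of each rule over the protocol's three dose levels (6.5, 5.5 and 4.5 mg/kg, Table 2-2). All events are Grade 3, non-hematological, and neither corneal nor infusion-related.

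**Path A: first event at 6.5 mg/kg, re-started at 6.5 mg/kg (allowed by Table 2-5).**

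| Event | Lead-in | Table 2-5 | Bullets, if a reduction is required | Figure 2-1, anetumab-specific list |
|---|---|---|---|---|
| Second, at 6.5 | 6.5 or 5.5 | Decrease: 5.5 from the current dose, or 4.5 if the extra level is counted from an assumed first reduction | 5.5 | Neither reduction-based stop met |
| Third, at 5.5 after one reduction | 5.5 or 4.5, if continuing is appropriate | Permanent stop | 4.5 | One reduction used and dose above 4.5, so neither reduction-based stop met; third appearance not listed |

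**Path B: first event at 6.5 mg/kg, reduced to 5.5 mg/kg.**

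| Event | Lead-in | Table 2-5 | Bullets, if a reduction is required | Figure 2-1, anetumab-specific list |
|---|---|---|---|---|
| Second, at 5.5 | 5.5 or 4.5 | 4.5 | 4.5 | Neither reduction-based stop met |
| Third, at 4.5 | 4.5, if continuing is appropriate | Permanent stop | No lower level | Stop if a reduction is required |

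Three things follow.

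1. At the second appearance the conflict is between keeping and reducing the dose, on both paths. It comes from the lead-in against the table. The table and the bullets agree on Path B.
2. At the third appearance on Path A, the lead-in read alone permits 5.5 mg/kg, the bullets point to 4.5 mg/kg, and the table stops treatment.
3. Nothing in the protocol ranks these texts. Section 7.3.2.1, for hematological events, says that the dose is to follow Tables 2-3 and 2-4; the non-hematological sentence grants discretion and only points to its table. Section 7.3.2.5, on permanent discontinuation, refers to Section 6.3.1.2, which concerns full screening failure, so it does not settle the matter.

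A secondary point: *appearance* is not tied either to the same toxicity or to any Grade 3 toxicity. Two different toxicities could be counted as one recurrence or as two first events.

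**The case against.** The best reply is that the table governs and the other texts fit round it. The lead-in cites Table 2-5 and applies only where continuing is appropriate. The amendment log says version 4.0 changed this sentence to cover the listed events and, in the same section, clarified Grade 1-2 discretion in the table, which suits a general sentence followed by a specific table. The bullets apply only to an event requiring dose reduction, and Section 7.3.2 lists reduction and permanent discontinuation as separate modifications, so a third appearance need not fall under them. Note c is a ceiling and gives no entitlement to two reductions. The Figure 2-1 items are each sufficient to stop; none says that treatment must otherwise go on.

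Much of this stands. A reader might infer that the bullets and note c require 4.5 mg/kg at the third event, or that Figure 2-1 stops treatment for only two reasons. The wording supports neither: the bullets are conditional, note c is a limit, and the list has other stops.

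What does not fall away is that the protocol never states this hierarchy. The table marks discretion cell by cell, so its absence at the second appearance contradicts the lead-in. The condition about continuing does not say whether a third appearance makes it inappropriate. Even with the table in charge, the presumed earlier reduction and the missing Figure 2-1 entry remain. The unacceptable-toxicity item only sends the reader back to the section in question.

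**Conclusion.** The point holds as an internal inconsistency in the rules for recurrent Grade 3 non-hematological toxicity. It is clearest for a patient re-started at the same dose after event 1, reduced once after event 2, and then having event 3. The conclusion rests on the wording alone and takes no view on which clinical rule is right.

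Its size cannot be given as a number of patients. A reader might be tempted to use the earlier 6.5 mg/kg cohort in Section 3.1: 16 of 32 were reduced and 4 of those reduced again, so 16 - 4 = 12, or 12/32 = 37.5%, had exactly one reduction, which is 0.375 × 30 = 11.25 of 30. The documents do not support that estimate:

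- A patient reduced at event 1 goes to 4.5 mg/kg at event 2 under both the table and the bullets, so a single reduction does not mark the affected path.
- The same section reports corneal toxicity in 12 of 32 and says that it always led to dose reduction; corneal events are outside this rule.
- It is not an upper bound either, since a patient never reduced can meet the conflict at a second event.
- That cohort had ovarian cancer and mesothelioma.

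A reader might also infer an effect on response rate or time to progression. Nothing in the documents shows one, and the two-stage sample-size calculation does not depend on the dose rule. The supported consequences are patient safety, consistency between sites, and the counts of dose reductions and discontinuations due to adverse events.

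**What to change.** The sponsor and investigator should reconcile the lead-in sentence, Table 2-5, the step-down bullets and Figure 2-1 into one rule. The amended text should:

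- state which text takes precedence;
- make the discretion in the lead-in and in the table rows agree;
- word the second-appearance row so that it also covers a patient re-started at the same dose;
- say what applies at a third appearance when only one reduction has been used, and carry that into Figure 2-1;
- say whether *appearance* counts the same toxicity or any Grade 3 toxicity.

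The clinical content of the rule is theirs to decide. The cost is a wording amendment to one sentence, one table, the bullets and one figure, with no extra patients or procedures.
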